1.0 Introduction

1.1 Needed: Immediate and Accurate Risk Stratification for Lung Cancer

Lung cancer is the deadliest form of cancer, with a 5-year survival rate in the United States of 16%ⁱ. Currently, it is difficult to detect and diagnose lung cancer early enough for treatment to be effective. New, immediate, and non-invasive methods are needed to stratify the risk of this disease in its earliest stages. Fresh Medical Laboratories' bioconductance technology has demonstrated the potential to meet these requirements.

The current standard of care for the detection of lung cancer involves the use of CT chest scans to evaluate patients with lesions suspicious for lung cancer. While these scans provide important information about the location and size of lung lesions and raise suspicion of lung cancer, they have limited capacity to determine immediately the malignant or benign nature of the lesions they identify. In the screening setting, nearly 25% of all CT screens are "positive" for an indeterminate nodule; among these 94% of non-calcified nodules are determined to be benign.ⁱⁱ This presents a significant diagnostic challenge.^{iii,iv} Given the frequency of benign disease, routine biopsy in an indeterminate lesion cannot usually be clinically justified. Because of these constraints, current guidelines^v call for repeated CT scans over a period of months or years, in order to detect malignant growth in the detected lesion(s).

The NCI recently concluded a seminal, multi-center clinical trial in which three repeated CT screenings over a two-year period resulted in a 20.0% decrease in mortality for the high risk study cohort.^{vi,vii} While these results are promising, concerns remain about repeated radiation exposure and the persistent high rate of false positives, potentially leading to extended evaluation and/or unnecessary biopsy procedures. Most importantly, by the time the lesion has grown enough to suggest malignancy, it is too late to achieve optimal treatment outcomes. In addition, there are concerns about the shortage of clinical infrastructure to manage the numbers of patients that would screen positive for cancer^{viii}. The 2011 International Association for the Study of Lung Cancer Core Task Force and Screening Implementation Group^{ix} recommended the development of new technologies to stratify the risk of cancer patients with indeterminate pulmonary nodules. A fast, accurate and non-invasive technology that could immediately stratify the risk of lung cancer in patients with an indeterminate pulmonary lesion could provide invaluable life-saving clinical information as well as reduce prolonged anxiety and unnecessary procedures in patients with indeterminate lesions.

1.2 Fresh Medical Laboratories ProLung Test™

Fresh Medical Laboratories transthoracic bioconductance technology (ProLung Test™) has demonstrated the ability to differentiate patients with indeterminate lung lesions as seen by CT^x. The value of this innovation lies in its potential to efficiently stratify the risk of lung cancer in a non-invasive, non-radiating test that provides immediate results. The Fresh Medical Laboratories ProLung Test has been determined to be non-significant risk by previous IRBs. To date, 160 patients have been evaluated for safety; all completed the entire measurement session and none discontinued measurement due to discomfort or an adverse event^{xi}.

2.0 Study Objectives

2.1 Objectives and Aims

The primary Study hypothesis is that the ProLung Test will demonstrate safety and efficacy in the risk stratification of patients with pulmonary lesions identified by CT that are suspicious for lung cancer. A statistically significant result will indicate that patients with a high ProLung Test result have a greater risk of developing lung cancer than patients with a low test result.

There are three Specific Aims of this study:

1. Optimize and confirm the stability of the ProLung Test risk-stratification algorithm in patients with a diagnosis.
2. Externally validate the efficacy of the ProLung Test risk-stratification algorithm by comparing the test result to the conclusive patient diagnosis.
3. Assess the safety and tolerability of the ProLung Test procedures.

3.0 Study Design

This Study consists of two distinct phases, Stabilization and Validation. The Study will collect data from multiple sites (3 to 20), and each site may enroll patients and collect data for the Stabilization and Validation Phases with a minimum of three sites for the Validation Phase. In this multi-center Study, the patient's known diagnosis (of either a malignant or benign outcome) will be compared to the ProLung Test results. The patient's diagnosis is determined by tissue biopsy, surgical resection or by CT follow-up detecting significant nodule growth during a 1 year time frame. This Study follows the National Comprehensive Cancer Network definition for nodule growth. Nodule growth is defined as: 1) for nodules 15 mm or smaller: an increase in mean diameter of 2 mm or more in any nodule or in the solid portion of a part-solid nodule when compared with the baseline scan, or 2) for nodules 15 mm or more: an increase of 15% in mean diameter when compared with the baseline scan. Mean diameter is the mean of the longest diameter of the nodule and its perpendicular diameter^{xii}. If no significant growth is detected and the nodule is not definitively diagnosed by biopsy or surgical excision, the outcome will be considered benign unless indicated otherwise in the patient's medical record.

3.1 Stabilization Phase

The objective of the Stabilization Phase is to optimize and confirm the stability of the ProLung Test risk-stratification algorithm in patients with a diagnosis (Specific Aim 1). In this open multi-center Study, the patient's known diagnosis (of either a malignant or benign outcome) will be compared with the Algorithm. Certain components of the Algorithm may be adjusted or optimized to improve overall performance of the ProLung Test in the Study population.

Initially, 100 patients will be enrolled into the initial cohort of the Stabilization Phase. If required by the Sponsor, up to an additional 100 patients, in groups of 25 patients, may be enrolled in the Stabilization Phase until the Algorithm achieves stability as determined by the Sponsor. Once Algorithm stability has been determined and confirmed by the Sponsor, the risk stratification Algorithm will be locked for the

Validation Phase. Data from the Stabilization Phase will also be utilized to assess the safety and tolerability of the ProLung Test procedures.

3.2 Validation Phase

The objective of the Validation Phase is to externally validate the efficacy of the ProLung Test risk-stratification Algorithm by comparing the test result to the conclusive patient diagnosis (Specific Aim 2). The risk stratification Algorithm result is recorded and locked for this Phase.

The Validation Phase is blinded as follows:

Sponsor's Statistician is blinded from the patient's diagnosis outcome (malignant, benign or inconclusive). The patient's ProLung Test results will be provided to the Sponsor and/or Statistician.

Site clinical study team, including the PI, study coordinators, and ProLung Test operators, is blinded from the ProLung Test risk stratification algorithm results. At each site, the patients' diagnoses are accessible by the site clinical study team.

Initial Study enrollment in the Validation Phase will be 100 patients. To maintain the Study's statistical power, enrollment will continue until there is both a minimum of 100 subjects and a minimum of 40 ProLung high risk and a minimum of 40 ProLung low risk subjects are enrolled. If required by the Sponsor and/or Statistician, up to an additional 50 patients, in groups of 25 patients, may be enrolled in the Validation Phase prior to breaking the statistical blind. The statistical blind is broken at the end of Study recruitment and monitoring with approval by the Sponsor and/or Statistician.

If required by the Sponsor and/or Statistician, up to an additional 35 subjects may be enrolled in either the Stabilization or Validation Phase to replace the enrolled subjects that were lost to follow-up or fail the Study Inclusion / Exclusion Criteria.

3.3 Safety and Tolerability

To assess the safety and tolerability of the ProLung Test procedures, the Study will utilize the data from all patients enrolled in the Stabilization and Validation Phases. Information collected about adverse events and tolerability will be analyzed as described in sections 5.8 and 6.0 (Additional Data Collection and Adverse Events).

3.4 Study Sample Size

This Study may enroll a maximum of 200 in the Stabilization Phase and 150 in the Validation Phase. The Study may enroll a minimum of 100 in the Stabilization Phase and 100 in the Validation Phase. In the Validation Phase, the sample size has been determined to provide greater than 90% power to reject the primary study hypothesis.

3.5 Assignment to Study Phase

The site study teams will enroll patients sequentially into the Stabilization Phase. When the Sponsor has confirmed the stability of the ProLung Test risk-stratification Algorithm, the Stability Phase will be completed and the Validation Phase launch will be confirmed by written notice to each site clinical study team. Prior to enrollment in the Validation Phase, Study blinding will be established and monitored.

3.6 Monitoring

The study Sponsor will provide monitors to monitor Protocol compliance and provide guidance pertaining to the management of the Study.

3.7 Study Design Summary

Design Element	Stabilization Phase	Validation Phase
Patient Enrollment	100-200 patients	100-150 patients
Sites	3-20	3-20
Blinding and Breaking the Statistical Blind	Open phase - Optimize algorithm with known diagnosis	Blinded phase – Sponsor’s Statistician is blinded to diagnosis and site study team is blinded to ProLung Test results. The statistical blind is broken at the end of Study recruitment and monitoring with approval by the Sponsor and/or Statistician.
Primary Objectives:	Stability of ProLung Test risk stratification algorithm as confirmed by Sponsor.	Clinical efficacy in the risk stratification of patients with indeterminate lesions.
	Safety and tolerability	Safety and tolerability

4.0 Subject Selection and Participation

4.1 Inclusion Criteria

Subjects who meet all of the following criteria may be enrolled in this Study:

1. Subject is male or female, age 18 or older.
2. Subject has undergone CT scan of the lung(s) that indicates one or more nodules or lesions suspicious for lung cancer.
3. Subject’s pulmonary nodule or lesion is greater than 4mm. Size is determined by the largest nodule or lesion dimension identified from CT imaging.
4. Subject meets one or more of the following conditions:
 - indicated for a tissue biopsy

- indicated for surgical resection of the lung
- 5. Subject must be able to receive a ProLung Test
 - within 60 days of abnormal CT (*Inclusion Criterion 2 & 3*)
 - within 60 days prior to the tissue biopsy or surgical resection (*Inclusion Criterion 4*).
- 6. Subject is capable of understanding and agreeing to fulfill the requirements of this Protocol.
- 7. Subject has signed the IRB/IEC approved Informed Consent Form ("ICF").

4.2 Exclusion Criteria

The following criteria will disqualify a subject from enrollment into this Study:

1. Subject has an implanted electronic device in the chest.
2. Subject receiving therapy for suspected chest infection such as fungal infection or tuberculosis.
3. Subject with diagnosed malignancy other than lung cancer, non-melanoma skin cancer or any cancer in which the Principal Investigator does not suspect metastatic disease to the lung, who has 2 or more suspicious pulmonary nodules.
4. Subject has received an invasive medical or surgical procedure within the thoracic cavity within 30 days prior to the ProLung Test or within the previous 14 days for a bronchoscopic procedure.
5. Subject presents with an anomalous physical or anatomical condition that precludes ProLung Test measurement.
6. Subject will have undergone unusually strenuous exercise within 24 hours.
7. Subject who has significant systemic diseases such as uncontrolled diabetes, advanced heart failure, or a recent myocardial infarction, or other medical condition such as severe morbid obesity that in the judgment of the Principal Investigator would make him/her unsuitable for the Study.

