## **Analysis Summary**

**Study Title:** A Multi-Center Trial of the ProLung Test (Transthoracic Bioconductance Measurement) as an Adjunct to CT Chest Scans for the Risk Stratification of Patients with Pulmonary Lesions Suspicious for Lung Cancer (Protocol PL-208)

**Primary Objective:** To demonstrate that the ProLung Test can assist in the assessment of patients presenting with indeterminant CT scans.

**Primary Endpoint:** The coprimary endpoints are the Positive Predictive Value (PPV) and Negative Predictive Value (NPV)

**Secondary Endpoints:** Co-secondary endpoints of sensitivity and specificity of the ProLung Test and the sum of PPV and NPV

**Additional Endpoints:** Additional Effectiveness Endpoint Analyses - Subgroup Analyses of NPV, PPV, sensitivity and specificity.

**Patient Population:** Males and females aged 18 years and older with a CT scan of the lungs that indicates one or more nodules or lesions suspicious for lung cancer.

**Study Design:** A single arm multicenter study of subjects with CT scans with nodules of undetermined significance and known diagnosis to be used to validate the ProLung Test to stratify the positive risk of lung cancer.

**Number of Patients:** 174 subjects with paired ProLung test result and a biopsy or radiological stability diagnosis for lung cancer.

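### No eligibility or analysis rule ties the ProLung Test to the first tissue diagnosis, so already proven lung cancers can enter the completed-case set and shift both PPV and NPV

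*Protocol*

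**What the plan says.** **Entry.** Protocol 4.1, Inclusion 4, is met by a biopsy indication or, on its own, by being "indicated for surgical resection of the lung". Inclusion 5 sets two time windows for the test: "within 60 days of abnormal CT" and "within 60 days prior to the tissue biopsy or surgical resection". The second refers to the procedure for which the patient is indicated.

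**Exclusions.** Protocol 4.2, Exclusion 4, bars an invasive thoracic procedure in the 30 days before the test, or "within the previous 14 days for a bronchoscopic procedure". Older procedures are allowed, whatever they showed. Exclusion 3 begins "Subject with diagnosed malignancy other than lung cancer", so proven lung cancer falls outside it.

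**Analysis sets.** Protocol 4.3.2 removes subjects with lost records, an inconclusive biopsy or incomplete test data. A diagnosis made before the test is not on that list. Protocol 8.1 asks for a biopsy within 60 days of the test without saying on which side. SAP IV.B asks only for a test result paired with a tissue result or radiological stability, and gives no timing.

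**Intended population and order.** Protocol 3.7 states the Validation objective for indeterminate lesions, and the SAP Analysis Summary refers to "nodules of undetermined significance". Protocol 5.9 has active participation end before the lung biopsy. Protocol 8.1 defines sensitivity and specificity by biopsy results that come after the test.

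**The concern.** The test is meant to help when the nature of a lesion is unknown. A subject whose lesion is already proven malignant is outside that population, yet would count like any other in the primary analysis. Such a subject can be a true positive or a false negative, but never a false positive or a true negative. Including these subjects raises prevalence, and SAP V.A.1 itself notes that lower prevalence lowers PPV and raises NPV. Because PPV and NPV are coprimary, both would then describe a mix of undiagnosed and already diagnosed patients.

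**Working it through.** **1. Can such a subject qualify?** Take an illustrative timeline: CT on day 0, malignant bronchoscopic biopsy on day 10, ProLung Test on day 30, resection on day 45.

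- Inclusion 4: indicated for resection. Met.
- Inclusion 5: test 30 days after CT and 45 − 30 = 15 days before resection; both limits are 60 days. Met.
- Exclusion 3: the malignancy is lung cancer. Not triggered.
- Exclusion 4: bronchoscopy 30 − 10 = 20 days before the test; the limit is 14. Not triggered.
- Protocol 4.3.2, Protocol 8.1 and SAP IV.B: complete test, definitive tissue within 60 days, paired result. Kept.

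The same holds after another thoracic procedure more than 30 days before the test.

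**2. The SAP's expected figures.** SAP V.A.1 gives 111 malignant and 63 benign cases, with TP 78, FN 33, FP 22 and TN 41.

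- PPV = 78/(78 + 22) = 0.780 (SAP 0.778).
- NPV = 41/(41 + 33) = 0.554 (SAP 0.551).
- Sensitivity = 78/111 = 0.703. Prevalence = 111/174 = 0.638.

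The SAP's figures reproduce within rounding of the counts.

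**3. Removing k pre-proven cancers.** The documents do not give k; 11, 22 and 33 (about 10%, 20% and 30% of 111) are assumed. Sensitivity is assumed equal in these subjects, and no benign case is removed. Then TP = 0.703 × (111 − k), FN = 0.297 × (111 − k), PPV = TP/(TP + 22) and NPV = 41/(41 + FN). Power is for the one-sided exact binomial test at 0.025 (SAP X.A) with the goals fixed at 0.638 and 0.381, using rounded numbers of positive and negative tests.

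| k | TP | FN | Prevalence | PPV | NPV | PPV power | NPV power |
|---|---|---|---|---|---|---|---|
| 0 | 78.0 | 33.0 | 0.638 | 0.780 | 0.554 | 0.86 | 0.85 |
| 11 | 70.3 | 29.7 | 0.613 | 0.762 | 0.580 | 0.66 | 0.91 |
| 22 | 62.5 | 26.5 | 0.586 | 0.740 | 0.608 | 0.45 | 0.96 |
| 33 | 54.8 | 23.2 | 0.553 | 0.714 | 0.639 | 0.26 | 0.98 |

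**4. Where the PPV decision turns, with the goal fixed at 0.638.** Removing j known true positives leaves (78 − j)/(100 − j). The exact lower 97.5% limits are:

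- j = 0: 78/100, limit 0.686, passes.
- j = 14: 64/86, limit 0.639, passes (p = 0.024).
- j = 15: 63/85, limit 0.635, fails (p = 0.029).

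Fifteen true positives correspond to 15/0.703 ≈ 21 known cancers.

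**5. If the goal moves with the case mix.** The PPV goal of 0.638 equals 111/174. If the goal is assumed to follow prevalence (0.638, 0.613, 0.586, 0.553), PPV power for k = 0, 11, 22, 33 is 0.86, 0.87, 0.80 and 0.81.

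**6. If the test detects proven cancers more often.** Assume sensitivity 0.85 in 22 such subjects. TP in the rest is 78 − 18.7 = 59.3, so PPV = 59.3/81.3 = 0.729. Sensitivity in the undiagnosed is 59.3/89 = 0.67.

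**The case against.** The documents do presume that the test comes first. Inclusion 5 puts it before the indicated procedure, Protocol 5.9 puts it before the lung biopsy, and Protocol 8.1 speaks of later biopsies. A reader might infer that nothing requires the test to precede biopsy; that goes too far. What stands is that none of this text refers to the first tissue diagnosis, and that 5.9 and the definitions in 8.1 are neither eligibility criteria nor analysis exclusions.

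A reader might see a deliberate route for proven cancers. The text does not show one. Exclusion 4 reads as a washout and equally admits patients whose earlier bronchoscopy was non-diagnostic.

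A reader might take the effect as one-sided in the device's favour. It is not: at fixed accuracy NPV falls as PPV rises, and both must succeed (SAP VI).

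A reader might say that 15 subjects decide the trial. That calculation keeps a goal which SAP V.A.1 set as achievable for the 111/63 mix. If the goal tracks prevalence, most of the power loss disappears (step 5). That tracking is itself an assumption, and the SAP as written has a fixed goal.

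Finally, since "diagnoses are accessible by the site clinical study team", a reader might suspect that operators who know the diagnosis could steer the measurement. Operators are blinded to the algorithm result, the algorithm is locked, and the device sequences the measurement points (Protocol 3.2, 5.7). The documents show no way to steer a score that the operator cannot see.

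**Conclusion.** The gap is real and should be fixed, but it does not show that the trial is invalid. No eligibility or analysis rule ties the test to the first tissue diagnosis of the study lesion, so 4.1, 4.2 and SAP IV.B do not enforce the order and population that Protocol 3.7, 5.9, 8.1 and the SAP Analysis Summary assume.

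If 11 to 33 of the 111 cancers were already proven, their presence makes PPV about 0.02 to 0.07 higher (0.780 against 0.762–0.714) and NPV about 0.03 to 0.09 lower (0.554 against 0.580–0.639). This rests on the SAP's expected counts, equal sensitivity in both groups and no benign cases removed. With the goal fixed, about 15 known true positives could change the PPV decision, subject to the caveat on how the goal was set. The true number is not reported and could be zero.

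**What to change.** Before unblinding, reconcile Protocol 4.1, 4.2 and SAP IV.B with Protocol 3.7, 5.9, 8.1 and the SAP Analysis Summary:

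1. Add to SAP IV.B that the completed-case set requires the ProLung Test date to precede the first definitive tissue diagnosis of the study lesion. Apply the rule whether that diagnosis was malignant or benign. Subjects with only a non-diagnostic earlier procedure stay in.
2. Report how many subjects were diagnosed before the test, and give PPV and NPV with and without them.
3. If the set changes, re-derive both performance goals and the power for the resulting case mix, also before unblinding.

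A new enrolment exclusion would not be enough, because SAP V.A.1 already counts the diagnoses of the 174 validation subjects.

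**Cost.** One SAP sentence and a date check on biopsy and pathology reports already collected (Protocol 5.1, 5.10). If such subjects exist, there are fewer malignant cases, PPV is somewhat lower and PPV power falls unless the goal is re-derived; NPV rises at fixed accuracy. If there are none, the check settles the point at almost no cost.

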4.3 Subject Discontinuation

In accordance with the Declaration of Helsinki, subjects are free to discontinue the Study at any time for any or for no reason. Should a subject decide to withdraw, every effort should be made to obtain information about the reason(s) for discontinuation. The Principal Investigator also has the right to withdraw subjects from the Study at any time at his/her discretion.

4.3.1 Events Necessitating Premature Discontinuation

The occurrence of any one of the following events may necessitate premature discontinuation of a subject from the Study:

- Subject develops any of the exclusion criteria after enrollment.
- Subject is unwilling to continue in the Study.
- Subject does not comply with the Study Protocol.
- Subject being followed by CT for nodule growth who does not receive a follow-up CT by their 1-year enrollment anniversary or within 60 days after their 1-year enrollment anniversary.

- Principal Investigator decision.

4.3.2 Events Eliminating Subjects from Primary Analyses

- Incomplete or lost medical records.
- Inconclusive biopsy result.
- Incomplete ProLung Test data.

5.0 Study Procedures

5.1 Study Procedures Summary

Patient Visit:

- Obtain demographics
- Obtain smoking history, and details of industrial exposure
- Obtain recent medical and surgical history
- Record concomitant medications (most recent 2 weeks)
- Conduct physical examination
- Perform ProLung Test. Adverse Event assessment
- Administer Tolerability Questionnaire
- Print out ProLung Test summary report for inclusion in patient's source documentation

Patient Data and Source Documentation Collection:

- Transmit patient data to Sponsor weekly as patients complete ProLung Testing
- Obtain radiological reports including CT, chest x-ray, follow-up CT, PET, and MRI.
- Obtain surgical report
- Obtain biopsy report
- Obtain pathology report

